# **Using TMS to Increase Executive Function in Older Adults**

**NCT02767323**

## **Study Protocol**

**Date of Approval:**  
**01/19/2021**

Behavioral research on aging has mapped contrasting patterns of decline and stability in cognition across the adult lifespan. Both cross-sectional and longitudinal studies find robust declines in working memory (WM), which describes the storage and manipulation of temporary representations of information that was just experienced or just retrieved from long-term memory. The current proposal seeks to use a functionally-guided brain-stimulation (repetitive transcranial magnetic stimulation or rTMS) paradigm to modulate the working memory functions of the left dorsolateral prefrontal cortex (DLPFC) or left parietal cortex (PC). The research team carries the expectation that, active rTMS over the DLPFC and PC will improve WM performance compared to sham rTMS; and since older adults rely more heavily on prefrontal function than young adults, older adults will benefit more from DLPFC stimulation than the young. Differential rTMS modulation of WM performance between young and older groups will provide causal evidence for compensatory processing, and help fill out our understanding of the neural basis of sustained, successful performance in aging. While we have previously demonstrated WM effects from stimulating the lateral occipital cortex (LOC), a specific region within the occipital PC, a finding of relative enhancement of executive processing with PFC stimulation- an enhancement that is long lasting and that transfers to executive processing beyond WM- is a key to development of noninvasive brain stimulation treatment of cognitive deficits, as this more frontal brain region is closely associated with neuroplastic abilities like executive processing. This will be tested through three aims, in which rTMS will be applied over the DLPFC (Aim 1a), the LPC (Aim 1b) or both the DLPFC and the LPFC in alternating blocks (Aim 1c). We have 3 key objectives:

**Primary Objective:** To evaluate the ability of rTMS applied to the DLPFC, the PC to enhance working memory performance in both younger and older adults.

**Primary Endpoint:** We expect performance enhancements between active and sham rTMS to PFC or PC to increase as the task becomes more difficult, as executive control processes are centered in this region.

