#### WM TASKS:

Two WM tasks will be performed a Delayed Response Alphabetization task (DRAT, Aim 1a, 1b, 1c) involving both maintenance and manipulation of information and a Delayed Response Maintenance Task (DRMT, Aim 1c) that only involved maintenance. Our implementation of the WM task for MRI consists of up to 10 runs of approximately 10-minute long letter-presenting blocks. Each trial begins with the presentation of a fixation cross during 5 seconds followed by the presentation of up to 9 uppercase letters arranged in a line. In the case where fewer letters are presented, all other positions are filled with asterisks. Stimuli are presented for up to three seconds before the screen is cleared. After a retention interval of 5 seconds, a probe stimulus is presented in the center of the screen for four seconds. The probe consists of the combination of a letter and a number, and which subjects are asked to answer. During this period subjects must press one of three keys indicating whether the number matches the position of the letter in the reorganized alphabetical order for the DRAT; or the serial position of the letter for the DRMT (Valid trials); or if the number does not match the letter position (Invalid trials); or if the letter did not belong to the array of letters (New, Aim 1a and 1b). Feedback is provided, at the end of each block as the overall accuracy. Tasks are performed with 1 (Hard, Aim 1c first cohort), 2 (Easy and Hard, Aim 1b and Aim 1c second cohort), or 3 (Easy, Medium, and Hard: Aim 1a) difficulty levels, defined as the number of letters presented on the screen and individually for each subject according to their performance during the screening visit. In rTMS sessions, the WM tasks will be run while stimulation is applied over the DLPFC (Aim 1a, Aim 1c) or the PC (Aim 1b, Aim 1c) either before the encoding (Aim 1a, Aim 1c) or during the delay period (Aim 1b, Aim 1c). Each block of trials will take about 10 minutes. To clarify all these conditions please refer to Figure 1 below.

	Group	Dosing	Timing	Site	Task	Difficulty	
Aim 1a	YA	100%rMT	Before the encoding	Frontal	DRAT	Easy	n= 29YA + 18 OA (6conditions/subj)
	OA	100%Eref 80%Eref	During the delay	Parietal	DRMT	Medium Hard	
Aim 1b	YA	100%rMT	Before the encoding	Frontal	DRAT	Easy	n= 15OA (4conditions/subj)
	OA	100%Eref 80%Eref	During the delay	Parietal	DRMT	Medium Hard	
Aim 1c Cohort 1	YA	100%rMT	Before the encoding	Frontal	DRAT	Easy	n= 15YA (4conditions/subj)

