Aim 1a: rTMS applied over the DLPFC either before the encoding or during the delay period of the Delayed Response Alphabetization Task (DRAT, a working memory task in which participants were asked to maintain and reorganize in alphabetical order an array of letter) will be performed by young and older healthy adults with three difficulty levels, during 4 rTMS visits. Since it is expected that Valid (trials in which the number matches the position of the letter in the reorganized alphabetical order) and Invalid (trials in which the number does not match the position of the letter) trials will lead to strong differences in accuracy, two ANOVAs will be performed separately on each trial condition, for reaction time and accuracy. The two ANOVAs will be conducted with Group (Younger or Older adults), as the between-subject factor; and Visit (Visit 3, Visit 4, Visit 5 and Visit 6), Difficulty (Easy, Medium, and Hard), Stimulation Timing (Pre and Post) and Stimulation Type (Active and Sham) as the within-subject factor. If no difference are found between the two groups, they will be collapsed and the ANOVA will be performed on the larger sample.

Aim 1b: rTMS applied over the PC during the delay period of the DRAT performed with two difficulty levels in older adults, comparing the effect of two stimulation intensities defined with electric field modeling (E-field). A repeated measure ANOVA will be performed with Task Condition (Valid and Invalid), Stimulation Type (Active and Sham), Stimulation Amplitude (80% and 100% Eref), and Task Difficulty (Easy and Hard).

Aim 1c: rTMS applied over the DLPFC and the PC in younger adults performing the DRAT and the Delayed Response Maintenance Task (DRMT, an additional WM task added to the design and involving only the maintenance of the array of letter). rTMS will be applied before the encoding period of the WM tasks, performed with either one difficulty level (Hard) or two difficulty levels (Easy and Hard) in younger adults. A repeated ANOVA will be conducted with Task Condition (Valid and Invalid), Difficulty levels (only for subjects who performed the task with Easy and Hard difficulty levels), WM task (DRAT and DRMT), Stimulation Site (DLPFC and PC), and Stimulation Type (Active and Sham).

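### Aim 1a gives the primary-endpoint interaction up to four unadjusted chances, names no deciding test, and cannot test whether the effect differs between Valid and Invalid trials

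*SAP*

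**What the plan says.** The protocol's Primary Endpoint is worded as an expectation: "We expect performance enhancements between active and sham rTMS to PFC or PC to increase as the task becomes more difficult". It names no outcome measure, trial type or test.

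The SAP (TMS data, Aim 1a) expects that Valid and Invalid "trials will lead to strong differences in accuracy", and on that ground "two ANOVAs will be performed separately on each trial condition, for reaction time and accuracy". Group is the between-subject factor. Visit is a within-subject factor, together with "Difficulty (Easy, Medium, and Hard), Stimulation Timing (Pre and Post) and Stimulation Type (Active and Sham) as the within-subject factor". Task Condition is not listed.

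For Aim 1b the SAP treats trial type differently: "A repeated measure ANOVA will be performed with Task Condition (Valid and Invalid), Stimulation Type (Active and Sham", with further factors. Aim 1c also lists Task Condition.

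Figure 1 of the protocol gives the Aim 1a sample as "n= 29YA + 18 OA (6conditions/subj", that is 47 people. Neither document states a significance level, sidedness, primary contrast or multiplicity rule for the TMS analyses.

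**The concern.** The endpoint is directional: the active-sham benefit should grow with difficulty. In the Aim 1a model this is Stimulation Type x Difficulty. Because the data are split by trial type and by outcome, the same hypothesis is tested several times, and nothing says how the results combine. One significant interaction could be reported as support for the endpoint, whichever fit it came from.

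The second gap concerns interpretation. If the effect is significant for Valid trials and not for Invalid trials, or the reverse, it would be natural to call it specific to one trial type. Separate fits cannot support that statement, because no term compares the two. The reason given for the split, a strong accuracy difference between trial types, concerns the main effect of trial type. A Task Condition factor would absorb it. It does not remove the need for an interaction test, and it does not bear on reaction time.

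**Working it through.** The plan gives no alpha, power or error-rate figure to reproduce, so everything below is illustrative.

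**Inputs.**
- From the documents: 29 younger + 18 older adults, three difficulty levels, two stimulation types, two trial types, two outcomes.
- Assumed: 0.05 per test, no true effect, equal correlation between outcomes of 0 to 0.9.

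**Number of fits.** 2 trial types x 2 outcomes = 4. Read literally, the sentence gives 2.

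**Independent tests.** P(at least one) = 1 - (1 - 0.05)^k.
- k = 4: 1 - 0.95^4 = 18.5%
- k = 2: 1 - 0.95^2 = 9.75%

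**Correlated tests.** Simulation of the 2-df Stimulation Type x Difficulty F test, using each subject's linear and quadratic scores of the active-sham difference, with Group in the model (error df 2 x 45 = 90).

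| Correlation | Four fits, any significant | Four fits, significant with Hard benefit above Easy |
|---|---|---|
| 0 | about 18.5% | about 9.6% |
| 0.5 | about 16% | about 8% |
| 0.8 | about 12% | about 6% |
| 0.9 | about 9.5% | about 5% |

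One test gives 5% and 2.5%. With two fits, the chance of any significant result is about 9.6% falling to 7%.

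**Ratio to a single test.**
- Four fits: 18.5/5 = 3.7 down to 9.5/5 = 1.9
- Two fits: 9.6/5 = 1.9 down to 7/5 = 1.4

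**False specificity.** Suppose the true effect is identical in both trial types, each fit has 80% power, and the tests are independent. One fit is significant and the other is not with probability 2 x 0.8 x 0.2 = 32%.

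**Power under the fix.** Noncentral t with 29 + 18 - 2 = 45 df.
- A linear contrast with 80% power at two-sided 0.05 has noncentrality 2.863. At 0.05/4 = 0.0125 its power is about 60%.
- If only one trial type responds, the three-way contrast has noncentrality 2.863/sqrt(2(1 - r)), where r is the Valid-Invalid correlation. At r = 0 this is 2.02 and power at 0.05 is 51%. At r = 0.5 it is 2.863 and power is 80%.
- Family-wise error at 0.0125 per test, if independent: 1 - (1 - 0.0125)^4 = 4.9%.

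**The case against.** The strongest reply has four parts.

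- **The deciding term is not wholly unspecified.** The endpoint wording points to Stimulation Type x Difficulty, and the Aim 1a model contains it. This stands for the term. It does not settle which outcome, trial type or alpha decides.
- **Splitting by trial type is defensible.** This stands. A reader might infer that the separate fits are themselves an error and should give way to one test averaged over trial types. The documents do not support that, and averaging is a trade-off. With equal effects in both trial types on one outcome, the averaged contrast (Holm over two outcomes, smaller p-value at 0.025) has 83% or 76% power at correlation 0.5 or 0.8. The separate fits at 0.0125 have about 77% or 70% for at least one significant result. If only one trial type responds, averaging has 26% or 22%, against about 60%.
- **The inflation depends on the reading.** A reader might infer that the error rate is always two to four times nominal. That holds only for four fits, which is an inference. On the literal two it is 1.4 to 1.9 times.
- **Counting every ANOVA term would exaggerate.** Five factors give 2^5 - 1 = 31 effects per fit and 4 x 31 = 124 in all. The endpoint concerns one term per fit, so that count does not measure the risk to the primary claim.

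**Conclusion.** The point holds, and should be corrected before analysis. As written, Aim 1a tests the endpoint's interaction in several fits without naming a deciding test, an alpha or a multiplicity rule, and it has no test of a difference between trial types. The false-positive chance is about 18.5% to 9.5% with four fits, or about 9.6% to 7% with two, against 5%. In the endpoint's direction with four fits it is about 9.6% to 5%, against 2.5%.

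These figures rest on an assumed 0.05 per test, no true effect and an assumed range of correlations, none of which the documents state. They show the size of the risk and are not the trial's actual error rate. The absence of a deciding rule and of a Task Condition factor does not depend on them.

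**What to change.** 1. Keep the separate Valid and Invalid fits and say plainly that there are four. In each, name the linear Stimulation Type x Difficulty contrast (Hard benefit minus Easy benefit) as the deciding test. Control the four tests together at two-sided 0.05 with Holm, so that the smallest p-value is judged at 0.0125. Claim support only if the effect is in the predicted direction.
2. Label all other terms secondary or exploratory, including those bearing on the expectation that "older adults will benefit more from DLPFC stimulation than the young".
3. For each outcome, add one model with Task Condition as a within-subject factor and report Stimulation Type x Difficulty x Task Condition. Make no claim that an effect is specific to one trial type unless this test supports it. Do not read a non-significant result as proof that the effect is shared.
4. Before Timing is kept as a within-subject factor, reconcile the documents. Figure 1's six conditions per subject equal 3 difficulties x 2 stimulation types; crossing two timings within subject would give 12. The protocol's WM Tasks text places Aim 1a stimulation ahead of encoding only, while the SAP lists Pre and Post.

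The cost is SAP wording and a little extra analysis, with no new data. A contrast with 80% power at 0.05 has about 60% at 0.0125. The three-way test is weak when Valid and Invalid scores are uncorrelated (51%, against 80% at correlation 0.5), which is why its non-significance must not be over-read.

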### Design and Procedures

This blinded, sham-controlled trial will feature a mixed model cross-over design, with rTMS Type (active, sham), Difficulty Level, Stimulation Location (DLPFC, PC), and Group (Young, Older adults) as factors. As such, this design reflects the fact that all subjects receive both active and sham rTMS applied to up to two different scalp locations during a WM task at up to three levels of difficulty. Study procedures are listed in **Table 1**. Up to thirty healthy young adults (age range: 18-35 years), thirty healthy older adults (age range: 55-80 years), will participate. In the initial session, which will take about 3 hours, participants will be consented and screened for the study, have a saliva sample taken, have TMS motor threshold determined, and then learn and practice the WM task. A structural and functional MRI will then be acquired within the screening visit or in a separate visit dependent on the participant's schedule. Cortical locations within PC and PFC to be used as targets for rTMS will be chosen from an analysis of subject-specific fMRI activations. Following the MRI, participants will take part in up to 5 sessions of rTMS (4 visits in Aim 1 and Aim 1b; and two visits in Aim 1c), each lasting up to 3 hours. TMS sessions will begin ~1 week after the MRI Session, to allow for time to process the imaging data, and within a 3-month period (Mondays thru Fridays), aiming to occur at the same time each day (+/- 2-3 hours for scheduling flexibility). Up to 5 rTMS sessions (involving active or sham rTMS and DLPFC (Aim 1a, Aim 1c), or PC targets (Aim 1b, Aim 1c) will use coil locations and rTMS device intensities based on realistic head modeling. Participants will report number of hours slept the previous night at each visit.

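### Aim 1a: the primary endpoint is an ordered increase over three difficulty levels, but the only planned test that matches it is a 2-df interaction F that ignores order and sign

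*SAP*

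**What the plan says.** The Protocol, under Primary Endpoint, states: "We expect performance enhancements between active and sham rTMS to PFC or PC to increase as the task becomes more difficult". That is a statement about order and direction.

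The Protocol, under WM TASKS, gives Aim 1a "3 (Easy, Medium, and Hard: Aim 1a) difficulty levels". Aim 1b and the second cohort of Aim 1c have two levels, and the first cohort of Aim 1c has one. Figure 1 lists Aim 1a as "n= 29YA + 18 OA (6conditions/subj", which makes it the only aim with both age groups.

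The SAP, TMS data, Aim 1a, says that "two ANOVAs will be performed separately on each trial condition, for reaction time and accuracy", so there are four combinations of trial type and outcome. It continues: "The two ANOVAs will be conducted with Group (Younger or Older adults), as the between-subject factor". The within-subject factors are Visit and "Difficulty (Easy, Medium, and Hard), Stimulation Timing (Pre and Post) and Stimulation Type (Active and Sham) as the within-subject factor".

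For Aim 1a the SAP gives no trend or other ordered contrast, no rule on the order of the means, no alpha or sidedness, and no sphericity correction. It does not say which ANOVA term tests the endpoint.

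**The concern.** Among the listed factors, the lowest-order term that speaks to the endpoint is Stimulation Type × Difficulty. It has (2 − 1)(3 − 1) = 2 numerator df. Its F statistic does not change if the three difficulty labels are permuted, so it responds equally to a gain that rises with difficulty, one that falls, and one that peaks at Medium.

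Two things are at stake. First, a significant F leaves the endpoint question open, and the SAP has no rule to close it. Second, if the gain does rise fairly evenly, spreading the test over 2 df gives up power that the same data could supply.

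The issue is confined to Aim 1a. With two levels the interaction has 1 df and its sign gives the direction.

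**Working it through.** The documents contain no power or sample-size calculation, so there is no stated figure to reproduce.

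**Inputs from the documents.** N = 29 + 18 = 47 (Protocol, Figure 1). Three difficulty levels and two stimulation types. Active and sham are compared within participant: the Protocol, Design and Procedures, says "all subjects receive both active and sham rTMS".

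**Assumptions.** Two-sided 5%. Each participant's active-minus-sham gain at each level is averaged over Visit and Timing. Group is retained, so the error df are 2(47 − 2) = 90 for the F and 47 − 2 = 45 for the contrast. Sphericity holds unless stated.

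**Formulas.** Let δ be the mean gain at each level and σ² the within-participant error variance of the gains.
- Omnibus: noncentral F(2, 90), λ = N Σ(δ − mean δ)² / σ², critical value 3.10.
- Linear contrast, weights −1, 0, +1: noncentral F(1, 45), λ_L = N (δ_Hard − δ_Easy)² / (2σ²), critical value 4.06.

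**Step 1: linear increase (0, a/2, a).** Σ(δ − mean δ)² = a²/2, so λ = λ_L.
- λ = 8.20: contrast 80.0%, omnibus 71.3%.
- λ = 10.98: contrast 90.0%, omnibus 83.9%.
- In reverse, λ = 9.96 gives the omnibus 80.0% and the contrast 87.0%.

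With the planned maximum of 30 + 30 = 60 participants the last comparison is almost the same (80.0% v 87.1%).

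**Step 2: increases that are not linear.** For a gain only at Hard (0, 0, a) or a step (0, a, a), Σ(δ − mean δ)² = 2a²/3, so λ_L/λ = (1/2)/(2/3) = 0.75. At λ = 9.96 the omnibus has 80.0% and the two-sided contrast 76.3%. At this effect size the contrast is ahead when the Medium gain lies between about 10% and 90% of the way from Easy to Hard.

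**Step 3: patterns in milliseconds.** Assume an SD of 100 ms for each gain and a correlation of 0.3, so σ² = 100² × (1 − 0.3) = 7000. A positive gain means benefit.

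| Gain at Easy/Medium/Hard | λ | Omnibus significant | λ_L | Contrast significant |
|---|---|---|---|---|
| 60/30/0 (falls) | 47 × 1800/7000 = 12.09 | 87% | 12.09 | 93%, all in the unfavourable direction |
| 0/60/0 (peak at Medium) | 47 × 2400/7000 = 16.11 | 95% | 0 | 5% |
| 0/0/50 or 0/50/50 | 47 × 1667/7000 = 11.19 | 85% | 47 × 2500/14000 = 8.39 | 81% |
| 0/80/50 (peak at Medium, Hard above Easy) | 47 × 3267/7000 = 21.93 | 99% | 8.39 | 81% |
| 0/−40/50 (dip at Medium) | 47 × 4067/7000 = 27.30 | over 99% | 8.39 | 81% |

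Rows 1 and 2 show that the omnibus F is often significant for patterns that contradict the endpoint. The last two rows show the contrast's own limit: it compares Hard with Easy and can pass when Medium is out of order.

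**Step 4: sphericity.** With no true effect, a correlation of 0.3 and SDs of the gain of 60/90/150 ms (ratio 2.5) or 50/100/200 ms (ratio 4), simulation puts the uncorrected omnibus type I error at about 6% and 7%. The contrast, with its own error term, stays at about 5%.

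**The case against.** The strongest objection is that the contrast is not uniformly better. The endpoint says only that the gain increases; it does not promise equal steps. For two patterns consistent with it, Hard-only and step, the contrast loses about 4 points. This stands, and it rules out the inference that a true increase is always more likely to be found by the contrast.

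Second, the contrast does not establish monotonicity, as the 0/80/50 and 0/−40/50 rows show. This also stands, and is why the Medium estimate has to be reported.

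Third, a two-sided 1-df test also rejects for a falling gain, so the sign rule supplies the direction, and an analyst could equally inspect the means after a significant F. That is fair. A reader might infer that the sponsor would count a wrong-direction F as success; nothing in the SAP says so. What remains is that no such check is pre-specified, and inspecting three means after a 2-df test is not itself a test of the increase.

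Fourth, the SAP never designates Stimulation Type × Difficulty as the endpoint test. This is correct: the mapping is an inference, although no listed term fits better.

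Fifth, one might infer from the missing sphericity correction that the p-values are invalid. The documents give no variances, and even SD ratios of 2.5 to 4 move the error rate only from 5% to about 6–7%. This is a minor matter.

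**Conclusion.** The point holds as a mismatch between endpoint and test, limited to Aim 1a. A significant Stimulation Type × Difficulty F would not by itself show that the gain rises with difficulty, and the SAP offers nothing further that would. This part does not depend on any assumed SD.

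The effect on power is moderate and conditional. With n = 47 and two-sided 5%, a roughly linear increase is detected about 71% (84%) of the time by the F and 80% (90%) by the contrast. A Hard-only or step increase favours the F by about 4 points. The calculation works on gains averaged over Visit and Timing, so it approximates the full ANOVA in the SAP.

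The documents do not support saying that the planned F has a materially inflated error rate, or that the SAP has named it as the primary test. A planned contrast is a worthwhile and cheap improvement; its absence does not invalidate the plan.

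**What to change.** Add to the SAP, TMS data, Aim 1a:

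- **Endpoint test.** For each participant compute (active − sham at Hard) minus (active − sham at Easy), averaged over Visit and Stimulation Timing as delivered. Test its mean on 1 df with its own error term, retaining Group as in the plan.
- **Scope and direction.** Apply it to Valid and Invalid trials and to reaction time and accuracy, as the SAP already lists. State the favourable direction for each outcome: higher accuracy, lower reaction time.
- **Reading rule.** Claim support for the endpoint only if the sign is favourable. Report the Medium gain with its interval next to the contrast, because the contrast does not prove monotonicity.
- **Omnibus interaction.** Keep it as supportive, with a Greenhouse-Geisser correction.

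State alpha and sidedness at the same time. The contrast does not settle multiplicity: four tests at 5%, if independent, give 1 − 0.95⁴ = 18.5%.

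Before writing the averaging rule, reconcile Figure 1 with the SAP. Six conditions per participant equals 3 difficulties × 2 stimulation types, which leaves no room for Timing crossed within participant as the SAP lists it.

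The cost is a short paragraph and no new data. The downsides are slightly lower power for Hard-only or step patterns and low sensitivity to non-monotone ones; the supportive omnibus test partly covers both.

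### Aim 1a drops Group and pools young and older adults when no group difference is found, with no stated trigger and with non-significance read as sameness

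*SAP*

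**What the plan says.** The SAP, under TMS data, Aim 1a, sets out the initial model "with Group (Younger or Older adults), as the between-subject factor". Visit, Difficulty, Stimulation Timing and Stimulation Type are the within-subject factors. Valid and Invalid trials are analysed apart: "two ANOVAs will be performed separately on each trial condition, for reaction time and accuracy". The paragraph ends with the collapse rule: "If no difference are found between the two groups, they will be collapsed and the ANOVA will be performed on the larger sample".

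Among the TMS ANOVAs only Aim 1a includes both age groups. Aim 1b is in older adults and Aim 1c in younger adults.

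The protocol's opening section expects that "older adults will benefit more from DLPFC stimulation than the young" and gives that contrast a specific role: "Differential rTMS modulation of WM performance between young and older groups will provide causal evidence for compensatory processing". The Primary Objective is to see whether rTMS can "enhance working memory performance in both younger and older adults". Figure 1, under WM TASKS, gives the Aim 1a sample as "n= 29YA + 18 OA (6conditions/subj)".

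**The concern.** There are two faults.

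- **The trigger is undefined.** A group difference could mean the Group main effect, Group × Stimulation Type, or any term containing Group. The rule does not say which of these decides, at what alpha, or whether the decision is taken once or separately for each trial condition and outcome. Two analysts following the SAP could reach different final models from the same data.
- **Absence of a finding is taken as absence of a difference.** The rule follows an ANOVA and has no equivalence margin, so it can only mean that a test was not significant. With 29 against 18 subjects that is weak evidence that the groups respond alike.

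What is at stake is the age question. Once Group is dropped, an active-sham effect cannot be attributed to young adults, older adults or both. Yet the Primary Objective names both groups, and the protocol treats the difference between them as its evidence for compensation.

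**Working it through.** The documents state no alpha, effect size, SD or power for this analysis, so there is no planned figure to reproduce. The calculations below size the problem under stated assumptions.

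**Inputs.** 29 young and 18 older adults (Protocol, Figure 1). Assumed: one active-minus-sham score per subject, unit SD in each group, two-sided alpha 0.05.

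**How many terms could trigger the rule.** Five factors fully crossed give 2^5 − 1 = 31 effects per ANOVA. Of these, 2^4 = 16 contain Group, and 2^3 = 8 contain both Group and Stimulation Type. Two trial conditions by two outcomes gives 4 ANOVAs, hence up to 64 tests containing Group.

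**Precision of the group contrast.**
- SE = √(1/29 + 1/18) = 0.300 SD
- t(0.975, 45 df) = 2.014
- 95% CI half-width = 2.014 × 0.300 = 0.604 SD

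**How often truly different groups are collapsed.** Power comes from the noncentral t with 45 df and noncentrality d × √(29 × 18/47). If Group × Stimulation Type alone decides, the collapse rate is 1 − power. If any of the 16 Group terms can block collapse, and the other 15 are null and independent, that rate is multiplied by 0.95^15 = 0.463.

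| True difference (SD) | Power | Collapse: Group × Type decides | Collapse: any of 16 blocks |
|---|---|---|---|
| 0.3 | 0.165 | 84% | 39% |
| 0.5 | 0.371 | 63% | 29% |
| 0.8 | 0.742 | 26% | 12% |
| 1.0 | 0.903 | 10% | 4% |

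If the Group main effect decides and overall means are equal, collapse occurs 95% of the time, however large the Group × Stimulation Type difference. With no true group difference anywhere, collapse occurs 95% of the time if one term decides and 0.95^16 = 44% if any of 16 can block it.

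**What the pooled effect estimates.** The weights are 29/47 = 62% young and 18/47 = 38% older. If only older adults benefit, by 0.5 SD, the pooled effect is 0.5 × 18/47 = 0.19 SD. If only the young benefit, by 0.5 SD, it is 0.5 × 29/47 = 0.31 SD. In a simulation of that second case (200,000 runs), the groups collapsed in 63% of runs, and the pooled test was significant in 53% of those, although older adults had no effect.

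**What pooling gains.** 95% CI half-widths:
- Group kept, older adults: 2.014/√18 = 0.475 SD
- Group kept, young adults: 2.014/√29 = 0.374 SD
- Group kept, equal-weight average: 2.014 × 0.150 = 0.302 SD
- Group kept, size-weighted average: 2.014/√47 = 0.294 SD
- Group dropped: 2.013/√47 = 0.294 SD, taking the same unit SD

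If the groups truly differ by d, that difference goes into the pooled residual. Its expected variance is (46 + (29 × 18/47) × d²)/46. At d = 0.5 this is 1.060, so the half-width with Group dropped is about 2.013 × √(1.060/47) = 0.302 SD, wider than the 0.294 SD with Group kept.

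**The case against.** The strongest reply is that harm is limited. The Group model is fitted first, so the age hypothesis is tested before any pooling, and nothing says its estimates go unreported. That is true, and it is why the point is not fatal. It does not tell the reader which result triggers pooling, or make a non-significant test evidence of sameness.

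Other points stand in part:

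- **Term counts.** The counts of 31, 16 and 8 assume a full factorial. Figure 1's six conditions per subject fit three difficulties by two stimulation types, so Timing may not be crossed within subject. There would then be 15 effects, 8 with Group and 4 with Group and Stimulation Type. The collapse rates where any Group term blocks would become about 58%, 44%, 18% and 7% (0.95^7 in place of 0.95^15). The trigger is no better defined.
- **Assumed sizes.** The rates depend on assumed differences in units of an unknown SD. At the protocol's ceiling of 30 per group, power at 0.5 and 0.8 SD would be 48% and 86%, instead of 37% and 74%. Independence and 15 null terms are also a simplification, since an age difference in overall performance would itself block collapse under the any-term reading.
- **Precision.** Against the equal-weight average, pooling is about 3% narrower (0.294 against 0.302 SD). That compares two different averages, and the gain is negligible.
- **Degrees of freedom.** The cost of one applies to two-level contrasts. Stimulation Type × Difficulty, with three levels, loses two (92 to 90).
- **A narrower remedy.** Collapse could be kept with a pre-specified term, outcome and equivalence margin. At 29 against 18, with a true difference of zero, two one-sided tests at 0.05 would have about 5% power for a 0.5 SD margin and 67% for 0.8 SD, so the rule could rarely be used at a tight margin.

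**Conclusion.** The concern holds and should be fixed. The textual defect does not depend on any assumed effect size: the SAP names no term, outcome, alpha or margin, and it drops Group from the only TMS ANOVA that can address the protocol's age prediction. Its size does depend on assumptions. With one active-minus-sham score per subject, unit SD, two-sided 0.05 and Group × Stimulation Type as the trigger, a true 0.5 SD group difference leads to pooling 63% of the time, and a 0.8 SD difference 26% of the time. Other readings of the trigger give very different rates, which is itself part of the problem. The pooled result then answers a question about a 62:38 mixture of ages, with no worthwhile gain in precision.

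**What to change.** Delete the collapse sentence and state that Group stays in every Aim 1a ANOVA whatever its p-value. From that model report, each with a 95% CI:

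1. the Group × Stimulation Type contrast, and its interaction with Difficulty;
2. the active-minus-sham effect within young adults and within older adults;
3. the effect averaged over the two groups, with the weighting (equal or by group size) stated in advance.

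Add that a non-significant group test will not be described as showing that the groups are equivalent.

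The cost is SAP wording and, for two-level contrasts, one error degree of freedom (46 to 45). No new data are needed, and an averaged effect using all 47 subjects remains available.
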